6.4. WINDOWING CONVENTIONS

No visit windows will be applied in this study and the scheduled assessments will be reported and analyzed as per eCRF collection.

6.5. STATISTICAL TESTS

The default significant level will be (5%); confidence intervals will be 95% and all tests will be 2-sided, unless otherwise specified in the description of the analyses. All significant p-values (i.e. < 0.05) will be flagged by means of an "*" for ease of review.

For presentation of summary statistics for quantitative and qualitative variables see Appendix 1; Programming conventions for outputs.

6.6. COMMON CALCULATIONS

For quantitative measurements, change from baseline will be calculated as:

• Test value at post-dose time point – pre-dose at each treatment period value.

Document: Z:\RPL554\UYA25849\Biostatistics\Documentation\SAP\Verona RPL554-CO-204 SAP v1.0

Author: [name] Version Number: 1.0

Version Date: [18OCT2018]

Template No.: CS_TP_BS016 Revision 5 Reference: CS_WI_BS005

Effective Date: 01Apr2018

Page 18 of 50

Peak effect will be calculated as:

Maximum value in the first 4 hours after dosing.

Average effect will be calculated as:

• FEV₁ AUC divided by the length of the time interval of interest.

Log-transformations will be performed on FEV₁ data:

- FEV₁ will be analyzed using multiplicative models, which means that data will be logged prior to analysis.
- The results will then be back-transformed to linear scale (treatment differences will thus be ratios of geometric means).
- Morning trough FEV₁ calculated as mean of the 11 and 12-hour FEV₁ measurements following the pre-evening dose.

6.7. SOFTWARE VERSION

All analyses will be conducted using SAS version 9.4.

7. STATISTICAL CONSIDERATIONS

7.1. ADJUSTMENTS FOR COVARIATES AND FACTORS TO BE INCLUDED IN ANALYSES

The following covariates are used in the analyses. For details of their inclusion in the models, see the specific analysis section.

- Randomized treatment (fixed).
 - RPL554 1.5mg
 - o RPL554 6.0mg
 - Placebo

Document: Z:\RPL554\UYA25849\Biostatistics\Documentation\SAP\Verona RPL554-CO-204 SAP v1.0

Author: [name] Version Number: 1.0

Version Date: [18OCT2018]

Template No.: CS_TP_BS016 Revision 5 Reference: CS_WI_BS005

Effective Date: 01Apr2018

Page 19 of 50

- Treatment period (fixed).
 - o Treatment period 1
 - o Treatment period 2
 - Treatment period 3
- Baseline value of analyzed variable (covariate).

7.2. MULTICENTER STUDIES

This study will be conducted by multiple investigators at up to 4 study centers, in US and UK. Randomization to treatment groups is not stratified by country/center.

7.3. MISSING DATA

Missing safety data will not be imputed, apart from partial date imputations as specified in Appendix 2. Missing efficacy data will be handled as described in section 15.1.2 and section 15.2.2 of this analysis plan. Partial date imputations will be handled as specified in Appendix 2.

7.4. MULTIPLE COMPARISONS/ MULTIPLICITY

Significance of treatment effect will be tested for the primary and secondary efficacy endpoints and will be done for each of the 2 doses of RPL554 against placebo, starting with the highest dose (6 mg). To this end, the fixed-sequence testing approach (Maurer et al., 1995; Westfall & Krishen, 2001) will be used.

Let i = 0, 1 and 2 represent increasing dose levels, 0 denoting placebo. Also, let μ_i , i = 0, 1 and 2, denote the mean change from baseline in peak FEV₁ at Day 3 (measured in first 4 hours after morning dosing) for placebo and each increasing active dose level, respectively. The primary null hypotheses are defined as:

H_i: $\mu_i - \mu_0 = 0$ and will be tested against the 2-sided alternative K_i: $\mu_i - \mu_0 \neq 0$, i = 1 and 2

Document: Z:\RPL554\UYA25849\Biostatistics\Documentation\SAP\Verona RPL554-CO-204 SAP v1.0

Author: [name] Version Number: 1.0

Version Date: [18OCT2018]

Template No.: CS_TP_BS016 Revision 5 Reference: CS_WI_BS005

Effective Date: 01Apr2018

Page 20 of 50

Finally, let p_1 and p_2 denote the marginal p-values obtained from the statistical tests associated with H_1 and H_2 (obtained from the model).

The fixed-sequence testing will begin with the null hypothesis corresponding to the highest dose versus placebo. If a statistically significant difference is found at the 2-sided α level of 5%, the testing will proceed with the next highest dose. Otherwise, testing stops and the remaining null hypotheses are accepted without testing.

This testing strategy can be written as the following stepwise algorithm:

- Step 1: If $p_2 \le \alpha$ reject H_2 and go to Step 2. Otherwise, fail to reject H_2 and H_1 and stop.
- Step 2: If $p_1 \le \alpha$ reject H_1 . Otherwise, accept H_1 .

The fixed-sequence procedure controls the family-wise error rate in the strong sense because, for each null hypothesis, the testing is conditional upon rejecting all hypotheses earlier in the sequence (Dmitrienko, et al., 2009).

Each secondary endpoint will be tested independently and nominally following a hierarchical testing of doses like the one used for the primary.

7.5. EXAMINATION OF SUBGROUPS

No subgroup analyses will be performed for this study.

8. OUTPUT PRESENTATIONS

Appendix 1 shows conventions for presentation of data in outputs.

The templates provided with this SAP describe the presentations for this study and therefore the format and content of the summary tables, figures, and listings to be provided by IQVIA Biostatistics.

9. DISPOSITION AND WITHDRAWALS

All patients who provide informed consent will be accounted for in this study.

Document: Z:\RPL554\UYA25849\Biostatistics\Documentation\SAP\Verona RPL554-CO-204 SAP v1.0

Author: [name] Version Number: 1.0

Version Date: [18OCT2018]

Template No.: CS_TP_BS016 Revision 5 Reference: CS_WI_BS005

Effective Date: 01Apr2018

Page 21 of 50

Patient disposition, withdrawals and reasons for exclusion from each analysis set and protocol deviations, including inclusion and exclusion criteria will be presented for all patients, including those with screen failures and summarized by treatment sequence. Number of patients treated and discontinued in each treatment period will also be presented. Discontinued patients are assigned to treatment period based on the last day of treatment + 1 from study start: treatment period 1, treatment period 2 (7 to 14 days after treatment period 1), treatment period 3 (7 to 14 days after treatment period 2). If the patient discontinued/withdrawn, he/she will be allocated to the last treatment period attended and last treatment administered.

All protocol deviations collected will be divided into critical, major or minor categories and will be assigned to the treatment group the patient is on according to when the protocol deviation occurred. Critical and/or major protocol deviations affect the integrity of the drug activity data and will be obtained by the clinical research associates (CRAs) and documented in a log. The deviations will be discussed at monthly calls with the sponsor to determine the accuracy of classification and severity and to determine if any changes are needed to the wording of the descriptions. Major deviations however, are discussed as soon as they arise.

Preliminary assignment to each analysis population (therefore whether a patient is included/excluded in each analysis population [excluding the PK and PK/PD analysis population) will be recorded in an EXCEL sheet by the IQVIA Biostatistician, with the reason for exclusion from each population indicated. The EXCEL sheet will be reviewed by Verona and assignments/comments will be discussed and an agreement should be reached prior to the Database Lock of the study. After agreement is reached, the EXCEL sheet should be authorized by means of a customer authorization form (CAF).

10. DEMOGRAPHIC AND OTHER BASELINE CHARACTERISTICS

Demographic data and other baseline characteristics (including screening disease characteristics) will be presented for the all analysis sets (RND, SAF, FAS, CAS, PK) by the treatment sequences. No statistical testing will be carried out for demographic or other baseline characteristics.

Document: Z:\RPL554\UYA25849\Biostatistics\Documentation\SAP\Verona RPL554-CO-204 SAP v1.0

Author: [name] Version Number: 1.0

Version Date: [18OCT2018]

Template No.: CS_TP_BS016 Revision 5 Reference: CS_WI_BS005

Effective Date: 01Apr2018

Page 22 of 50

The following demographic and other baseline characteristics will be reported for this study:

- Age (years)
- Sex
- Childbearing potential
- Race
- Ethnicity
- Height (cm)
- Weight (kg)
- BMI (kg/m²)
- Pre (prior to dosing at baseline)/post (post dosing at baseline) bronchodilator FEV₁ (both in liters and in percentage of predicted normal)
- Post-bronchodilator FEV₁/ forced vital capacity (FVC)
- FEV₁ reversibility test (mL and %)

10.1. DERIVATIONS

- Age (years) = (Randomization date informed consent date)
- Height (cm) = height (cm) (if recorded in cm) OR height (inches) x 2.54 (if recorded in inches)
- Weight (kg) = weight (kg) (if recorded in kg) OR weight (lbs) x 0.453592 (if recorded in lbs)
- BMI (kg/m^2) = weight (kg)/ height $(m)^2$

Demographic and other baseline characteristics without derivations are recorded on the eCRF and used as is on the eCRF.

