4.1 Inclusion Criteria

- 1. Sign an informed consent document indicating they understand the purpose of and procedures required for the study and are willing to participate in the study.
- 2. Male or female aged between 40 and 80 years inclusive, at the time of informed consent.
- 3. If male: must agree to meet the following from the first dose up to 1 month after the last dose of study medication:
 - Not donate sperm
 - *Either:* be sexually abstinent in accordance with a patient's usual and preferred lifestyle (but agree to abide by the contraception requirements below should their circumstances change)

Or: use a condom with all sexual partners. If the partner is of childbearing potential the condom must be used with spermicide and a second reliable form of contraception must also be used (e.g. diaphragm/cap with spermicide, established hormonal contraception, intra-uterine device)

If female: be of non-childbearing potential or use a highly effective form of contraception as defined in Section 14.1.

- 4. Have a 12-lead ECG recording at Screening and pre-dose in Treatment Period 1 showing the following:
 - Heart rate between 45 and 90 beats per minute
 - QT interval corrected for heart rate using Fridericia's formula (QTcF) ≤450 msec for males, and ≤ 470 msec for females
 - QRS interval ≤120 msec
 - No clinically significant abnormality including morphology (e.g. left bundle branch block, atrio-ventricular nodal dysfunction, ST segment abnormalities consistent with ischemia)
- 5. Have a Screening Holter report with a minimum of 18 hours recording that is able to be evaluated for rhythm analysis showing no abnormality which indicates a significant impairment of patient safety or which may significantly impair interpretation, including:
 - Significant arrhythmias including atrial flutter, atrial fibrillation, ventricular tachycardia
 - Any symptomatic arrhythmia (except isolated extra systoles)
 - Any sustained second or third-degree heart block
- 6. Capable of complying with all study restrictions and procedures including ability to use the study nebulizer and Respimat® correctly.
- 7. Body mass index (BMI) between 18 and 36 kg/m² (inclusive) with a minimum weight of 45 kg.
- 8. COPD diagnosis: Patients with a diagnosis of COPD as defined by the American Thoracic Society (ATS)/European Respiratory Society (ERS) guidelines (Celli and MacNee, 2004) with symptoms compatible with COPD for at least 1 year prior to Screening.

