6 STUDY PROCEDURES AT EACH VISIT

The study will consist of the following:

- Screening will take place in the period between 7 and 14 days prior to the first study treatment administration. Screening procedures may be performed as a single visit or more than one visit. Since the Holter monitor is to be removed after 24 hours, patients will return one day after placement.
- Three treatment periods, each 3 days in duration and separated by 7 to 14 days (from last dose of study medication on Day 3 of each treatment period)
- An end of study visit between 4 and 10 days after the completion of Treatment Period 3 Eligible patients may be re-screened at the discretion of the Investigator.

Repeat, rescheduled, and unscheduled visits and procedures are permitted at the discretion of the Investigator.

The overall schedule of assessments at each visit is shown in Table 3 and the schedule of assessments on each day of each treatment period is shown in Table 4. Assessments are listed by visit in Section 1.1 to Section 6.4 and are described in Section 7.

Post-dose assessments should be performed in the following order: 1) ECG, 2) vital signs, 3) pharmacokinetic blood sample, 4) spirometry (prioritized on the timepoint).

Verona Pharma plc CONFIDENTIAL Page 30 of 66

Table 3 Overall Schedule of Assessments at Each Visit in RPL554-CO-204

Procedures	Screening	(7 to	End of Study			
Frocedures	14 to 7 days before Randomization	Day 1	Day 2	Day 3	Day 4	4 – 10 days after Day 4 o Treatment Period 3
Informed consent	X					
Demographics including height and weight	X					
Medical/surgical and disease history	X					
Eligibility criteria	X	X[a]				
Physical examination	X (Full)	X (Brief)			X (Brief)	X (Full)
Vital signs	X	X	X	X	X	X
Safety laboratory tests: hematology and biochemistry	X				X	X
Safety laboratory tests: urinalysis	X					X
Viral serology	X					
Alcohol breath test	X					
Serum pregnancy test (females of childbearing potential)	X					
Urine pregnancy test (females of childbearing potential)	X	X				X
Chest X-ray (or in last 12 months)	X					
12-lead ECG	X	X	X	X	X	X
24-hour Holter monitoring	X			X		
Spirometry: Reversibility test	X					
Spirometry: Study measurements		X	X	X	X	X
Whole body plethysmography training	X					
Whole body plethysmography		X		X		
Inhalation training (nebulizer and Respimat®)	X	X				
Randomization		X[a]				
Tiotropium/olodaterol and RPL554 or placebo dosing		X	X	X		
Pharmacokinetic sampling				X		
Dyspnea scale		X		X	X	

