7.1.1 Demographic Variables

Demographic variables, including date of birth, sex, height, weight, BMI (weight [kg]/height [m]²), race and smoking status will be collected at Screening.

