11. SURGICAL, MEDICAL AND COPD/SMOKING HISTORY

Surgical and Medical History information will be presented in listings only, for the RND analysis set.

Document: Z:\RPL554\UYA25849\Biostatistics\Documentation\SAP\Verona RPL554-CO-204 SAP v1.0

Author: [name] Version Number: 1.0

Version Date: [18OCT2018]

Template No.: CS_TP_BS016 Revision 5 Reference: CS_WI_BS005

Effective Date: 01Apr2018

Page 23 of 50

• Surgical History will be coded by Medical Dictionary for Regulatory Activities (MedDRA) dictionary using the version specified in the data management plan.

- Surgical History conditions are defined as those conditions which stop prior to or at Screening.
- O Data captured on the Surgical Procedure History page of the eCRF will be presented by SOC (System Organ Class) and PT (Preferred Term).
- Medical History will be coded by MedDRA dictionary using the version specified in the data management plan.
 - Medical History conditions are defined as those conditions which stop prior to or at Screening.
 - Data captured on the Medical History page of the eCRF will be presented by SOC and PT.
- COPD/Smoking History data captured on the COPD and Smoking History page of the eCRF will be presented for the RND analysis set.
 - Duration of COPD calculated relative to date of first diagnosis (Randomization date first COPD diagnosis date)
 - Smoking history (current or former, including pack years). Pack-years = Number of packs per day x
 Number of years smoking

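### SAP 10.1 derives age from the randomization and consent dates with no date of birth, so the age line of the demographic tables would be wrong for every patient

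*SAP*

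**What the plan says.** SAP section 10 lists age in years first among the characteristics it reports and presents these data by treatment sequence for the RND, SAF, FAS, CAS and PK sets. Section 10.1 then gives the derivation: "Age (years) = (Randomization date informed consent date"). It names no other input and no conversion from days to years.

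The same section has a fallback to the recorded value, but a limited one: "Demographic and other baseline characteristics without derivations are recorded on the eCRF and used as is on the eCRF". Age has a derivation, so the fallback does not reach it.

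The protocol holds what a correct derivation needs. Section 7.1.1 collects the birth date at Screening ("Demographic variables, including date of birth, sex, height, weight" and further items). Inclusion criterion 2 in section 4.1 fixes the date at which age counts: "Male or female aged between 40 and 80 years inclusive, at the time of informed consent". SAP 3.3 declares no changes from the protocol, so nothing suggests that age was redefined on purpose.

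**The concern.** Age is the time elapsed since birth. A rule that uses only two trial dates, both falling within weeks of first dose, cannot produce it. The SAP is the programming specification for the tables, and here it states a definite rule that gives a wrong value. That differs from leaving a detail open.

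At stake is the description of the study population. A reader of the report would look to the age summary to see that the patients match the 40 to 80 year range, which SAP 3.1 itself repeats. Values from this rule would be meaningless for that purpose.

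**Working it through.** The plan states no age figure to reproduce, so the check evaluates the rule as written.

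**The operator.** No sign appears between the two dates in the text. The same gap occurs in SAP 11 ("Duration of COPD calculated relative to date of first diagnosis (Randomization date first COPD diagnosis date") and in the SAP 13.1 derivations. I read it as a minus sign lost from the PDF and do not count it as an error. In the COPD-duration line, restoring the minus gives a sensible quantity, because one operand is a date in the patient's history. In the age line, it gives randomization date minus consent date.

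**Inputs.**
- Randomization is pre-dose on Day 1 of Treatment Period 1 (Protocol 3.1).
- On the interval from Screening, Protocol section 6 says: "Screening will take place in the period between 7 and 14 days prior to the first study treatment administration".
- Consent is typically obtained before the Screening visit, so that prohibited medications can be stopped (Protocol 6.2). The gap from consent to randomization can therefore exceed 14 days. The documents give no upper figure; 30 and 60 days are assumed below to show the range.

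**Rule as written:** interval in days, divided by 365.25 to express it in years.

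| Consent to randomization | Years | Completed years |
|---|---|---|
| 7 days | 7 / 365.25 = 0.019 | 0 |
| 14 days | 14 / 365.25 = 0.038 | 0 |
| 30 days (assumed) | 30 / 365.25 = 0.082 | 0 |
| 60 days (assumed) | 60 / 365.25 = 0.164 | 0 |

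Without the division, the table would show the number of days under a heading of years. To return 40, the rule would need an interval of 40 × 365.25 = 14,610 days. No patient can obtain a value in the eligible range by this rule.

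**Corrected rule:** completed calendar years from birth to consent. With assumed dates, a patient born 1 September 1978 who consents on 1 September 2018 is 40. One born 10 September 1937 who consents on the same day is 80. Both fall at the limits of criterion 2, as they should.

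**A shortcut to avoid.** A common day-count version is the integer part of (consent date − birth date + 1) / 365.25. For a patient born 2 September 1978 who consents on 1 September 2018, the difference is 14,609 days, and (14,609 + 1) / 365.25 = 40.0, so the formula returns 40. That patient is 39 and turns 40 the next day. The shortcut therefore fails at the lower eligibility limit.

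**The case against.** The strongest reply is that this is an evident drafting slip. The line is labelled in years, and a programmer who saw values near zero would stop and ask. The surrounding text has also lost characters, which limits certainty about what the SAP line says in full. Both points are fair, and they bear on how likely the error is to reach a table. They do not make the rule correct: the comparable lines in SAP 11 and 13.1 lack only their operators, and nothing marks a missing birth date in this one.

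A reader might go further and infer that the 40 to 80 year criterion could not be checked at all. The documents do not support that. Sites assess the criteria at Screening and again before the first dose (Protocol 6.3 and 7.1.6), date of birth is on record, the protocol provides source verification and data checks (8.2 and 8.3), and SAP section 9 presents deviations from the inclusion and exclusion criteria separately. None of these relies on the SAP 10.1 formula.

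A reader might also infer that the trial's results are at risk. They are not. Age is absent from the covariates in SAP 7.1 and from the model in 15.1.3, SAP 7.5 plans no subgroups, and section 10 excludes testing of baseline characteristics.

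Finally, one might fault the plan for anchoring age at randomization, since a patient aged 80 at consent could be 81 by Day 1. The plan proposes no such derivation. For a purely descriptive table, age at randomization would be a legitimate choice. Consent is preferred in the fix only because criterion 2 uses it.

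**Conclusion.** The point holds as an error in a reporting rule. Applied literally, SAP 10.1 yields about 0.02 to 0.04 years for a consent-to-randomization interval of 7 to 14 days, and still 0 completed years at an assumed 60 days. The age line would be wrong for all patients in all five analysis sets.

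This rests on two readings: that the lost operator is a minus, and that no birth-date term was lost with it. The first has support in the parallel lines. The second cannot be proved, but nothing in the text points the other way.

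The consequence is confined to the demographic tables and anything programmed from the derived age. Site eligibility decisions and the efficacy and safety conclusions are unaffected.

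**What to change.** Replace the age line in SAP 10.1 with: age in years is the number of completed calendar years from date of birth to the date of informed consent; where only a partial birth date is held, use the age at consent recorded by the site. Specify a calendar comparison (year difference, less one if the birthday has not yet been reached) and do not use the day count with +1 divided by 365.25.

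The cost is one line of SAP wording, best settled before the demographic tables are programmed and in any case before database lock. The protocol already provides for collecting date of birth, so no new data are needed.

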11. SURGICAL, MEDICAL AND COPD/SMOKING HISTORY

Surgical and Medical History information will be presented in listings only, for the RND analysis set.

Document: Z:\RPL554\UYA25849\Biostatistics\Documentation\SAP\Verona RPL554-CO-204 SAP v1.0

Author: [name] Version Number: 1.0

Version Date: [18OCT2018]

Template No.: CS_TP_BS016 Revision 5 Reference: CS_WI_BS005

Effective Date: 01Apr2018

Page 23 of 50

• Surgical History will be coded by Medical Dictionary for Regulatory Activities (MedDRA) dictionary using the version specified in the data management plan.

- Surgical History conditions are defined as those conditions which stop prior to or at Screening.
- O Data captured on the Surgical Procedure History page of the eCRF will be presented by SOC (System Organ Class) and PT (Preferred Term).
- Medical History will be coded by MedDRA dictionary using the version specified in the data management plan.
 - Medical History conditions are defined as those conditions which stop prior to or at Screening.
 - Data captured on the Medical History page of the eCRF will be presented by SOC and PT.
- COPD/Smoking History data captured on the COPD and Smoking History page of the eCRF will be presented for the RND analysis set.
 - Duration of COPD calculated relative to date of first diagnosis (Randomization date first COPD diagnosis date)
 - Smoking history (current or former, including pack years). Pack-years = Number of packs per day x
 Number of years smoking

